 - o mean peripartum change in haemoglobin and haematocrit as well as haemoglobin drop > 2 g/dL,
 - o transfer to intensive care unit (ICU),
 - o or death from any cause.
- To assess potential adverse effects of TXA:
 - o Hemodynamic parameters,
 - o adverse gastrointestinal events, renal, hepatic, and coagulation function,
 - o and any venous or arterial thrombosis at any time during the woman's postoperative course.

METHODOLOGY

Research design

Open-label parallel randomized control trial.

Target population

Women undergoing caesarean sections at Sally Mugabe and Parirenyatwa Hospitals based on set inclusion and exclusion criteria.

Inclusion criteria

- Estimated gestational age of 37 weeks or more
- Live intrauterine foetus
- Elective or emergency caesarean delivery
- Signed informed consent

Exclusion criteria including any of the following factors or conditions identified prior to surgery

- History of coagulopathies or conditions predisposing them to thromboembolic phenomena,
- seizure history,
- autoimmune disease,
- placental abruption,
- placenta praevia,
- abnormally adherent placentae if identified on prenatal ultrasound,
- eclampsia or HELLP syndrome,
- known hypersensitivity to TXA,
- planned general anaesthesia,
- caesarean delivery for the second twin or second/third triplet(s) after vaginal birth of the first twin,
- poor understanding of English/Shona languages,
- those who have received anticoagulants in the week before delivery
- persons-under-investigation for COVID-19 and confirmed COVID-19 positive women.

Women will receive individual information in late pregnancy about the trial from obstetricians and midwives during antenatal clinic visits or from anaesthetists during the pre-caesarean visit, or both. Women may be pre-included (receive information and sign consent forms) for caesareans both before and during labour when the investigator considers that the woman is likely to have a caesarean delivery. The aim of pre-inclusion is to facilitate recruitment, particularly the recruitment of caesareans during labour, which may be decided upon and performed in emergency situations. Women recruited prior to emergency caesarean delivery (in labour) sign consent to have the caesarean section while in labour. We therefore consider that having received information about the trial during the antenatal period and on the labour ward, they will also be able to provide informed consent for inclusion into the trial at the same time.

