TXA obtained for the study will be kept in theatre. This is to ensure an uninterrupted supply of the drug for the study. The TXA vials will be kept in theatre in a locked drug cupboard accessible to the researcher and research assistants at the authorization of the sister in charge. A dispensing register for the drugs will be kept together with the drugs. Patient details and study number, amount of TXA dispensed and wasted will be entered into the study register for accountability and to guard against abuse.

Intervention

The participants in the intervention arm will receive generally from the anaesthetist or nurse anaesthetist TXA (1g), administered slowly (over 30 – 60seconds) at the time of skin incision. Participants in both the intervention arm and control group will receive the routine prophylactic 10 IU oxytocin intravenously at birth of the baby. All other aspects of management of the caesarean section will be identical in both arms (34).

Other aspects of the caesarean delivery

- The surgical team will decide on the administration of additional uterotonics and the management of PPH, in a manner consistent with local guidelines. In particular, the use of TXA for the treatment of PPH will be allowed and left to the practitioner's discretion according to the hospital protocol.
- Because the surgeon's level of experience may affect estimated blood loss during or after a caesarean delivery, the obstetrician's experience, categorized as senior resident medical officer, senior house officer, junior registrar, senior registrar or consultant will be recorded (34).

Assessment

Data will be collected and recorded on the data collection tool. Any adverse event will to be reported on the IRB adverse event reporting form.

Primary outcome measure

Estimated blood loss (EBL) will be determined using haematocrit, haemoglobin, and visual estimates.

Calculated estimated blood loss = estimated blood volume \times (preoperative haematocrit – postoperative haematocrit) / preoperative haematocrit. Where estimated blood volume (mL) = weight (kg) \times 85).

The calculation is an objective measure to estimate blood loss because of the inaccuracy of other methods used to determine blood loss and caesarean delivery(35).

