Preoperative haematocrit will be determined on the day before elective caesarean or on the day of emergency caesarean delivery. Postoperative haematocrit will be the haematocrit obtained by blood sampling at D2 (on the second morning after caesarean section). If haematocrit is not available at D2, then haematocrit at D3 will be considered; if it is also missing, then the postpartum haematocrit closest to D2 in the absence of transfusion will be considered (36,37).

All women who receive RBC transfusion for PPH between delivery and D2 postpartum are defined to have PPH and meet the criteria for the primary outcome. Calculated blood loss is impossible to determine for these women. Moreover, women only rarely receive an RBC transfusion for a blood loss less than 1000 ml. As a marker of significant maternal morbidity, RBC transfusion is considered equivalent or superior to blood loss greater than 1000 mL(25).

Although visual estimation is the method used frequently by anaesthetists to estimate blood loss, it has been demonstrated as inaccurate in repeated studies. The estimate of blood loss is affected by amniotic fluid as well. Its continued use in clinical practice is likely related to tradition and it being easily used. We will also take note of the visual estimate made by the anaesthetist, and by the operating surgeon, as this is the method used locally(6,38)(39)

Secondary outcome measures

Describing postpartum blood loss

1. Clinical

- a. Visually estimated blood loss
- b. proportion of women requiring supplementary uterotonic treatment
- c. incidence of postpartum transfusion
- d. mean number of RBC units transfused
- e. incidence of emergency surgery for PPH including caesarean hysterectomies
- f. incidence of hypovolemic shock related to PPH as determined by assessing BP and pulse
- g. incidence of transfer to ICU
- h. incidence of maternal death from any cause
- i. length of hospital stay.

2. Laboratory

- a. incidence of calculated blood loss > 500 mL and > 1500 mL
- b. mean total calculated blood loss
- c. mean peripartum change in haemoglobin (difference between haemoglobin before delivery and at D2)
- d. Haemoglobin drop > 2 g/dL (between haemoglobin before delivery and at D2) (34).

Describing adverse events

1. Clinical

a. Hemodynamic parameters (heart rate, blood pressure) 15, 30, 45, 60, and 120 min after delivery

- b. the occurrence of potential mild adverse effects of TXA in the operating room:
 - i. nausea
 - ii. vomiting

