Quantitative variables will be expressed, as appropriate, as means with standard deviations (and compared by Student's t-test) or as medians with interquartile ranges (compared by the Wilcoxon rank-sum test). Chi-square or Fisher's exact tests will be used, as appropriate, to compare categorical variables. The effects of TXA will be expressed as relative risks with 95% confidence intervals for categorical outcomes and as mean differences with 95% confidence intervals for quantitative outcomes. The results will also be expressed as absolute risk differences with 95% confidence intervals for binary outcomes.

Two specified subgroup analyses will examine the primary outcome in subgroups of women at high risk of PPH. The subgroups will include women who undergo a caesarean during labour and those who are at risk for PPH according to a composite definition (having at least one risk factor with an odds ratio of 3 or greater in the literature (34) history of any of PPH, hypertensive disorder of pregnancy, multiple pregnancy, or caesarean during labour). Moreover, prespecified subgroup analyses will examine the secondary outcomes in the subgroup of women who undergo a caesarean during labour. We will use the Benjamini–Hochberg procedure to adjust for multiple comparisons of secondary outcomes or subgroups (34). A statistical test may be significant by chance but in reality, not significant. The Benjamini-Hochberg method is used to control for this false discovery rate in statistical tests. Statistical analysis will be conducted using Stata v16. Feasibility

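### Optional gain in precision: haemoglobin change, haematocrit change and mean calculated blood loss are compared unadjusted, although each contains a pre-operative value that ANCOVA could use at no cost

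*Combined protocol and SAP*

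**What the plan says.** Under Statistical methods and data reporting, quantitative variables are summarised as means and compared by Student's t-test, or as medians and compared by the Wilcoxon rank-sum test. Treatment effects are to be given as relative risks for categorical outcomes "and as mean differences with 95% confidence intervals for quantitative outcomes". No regression or covariate model is named for any outcome. The only adjustment mentioned is Benjamini–Hochberg, for multiplicity.

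Three continuous secondary outcomes are built from a measurement before and one after surgery:

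- Haemoglobin and haematocrit change. The list of secondary outcomes has "mean peripartum change in haemoglobin and haematocrit as well as haemoglobin drop > 2 g/dL".
- Mean calculated loss. The laboratory list under Secondary outcome measures has "mean total calculated blood loss". Its formula, under Primary outcome measure, begins "Calculated estimated blood loss = estimated blood volume". The volume is weight × 85, multiplied by the fall in haematocrit as a fraction of the pre-operative haematocrit.

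The baseline is timed before surgery: "Preoperative haematocrit will be determined on the day before elective caesarean or on the day of emergency caesarean delivery". Tranexamic acid is given at skin incision, so treatment cannot affect a pre-operative sample.

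On transfusion the same section says "All women who receive RBC transfusion for PPH between delivery and D2 postpartum are defined to have PPH", and then "Calculated blood loss is impossible to determine for these women".

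**The concern.** A raw comparison of change scores fixes the slope of the post-operative on the pre-operative value at 1. ANCOVA estimates that slope from the data. In large samples with 1:1 allocation, ANCOVA is therefore never less precise, and it also removes chance imbalance in the baseline value. The pre-operative value is needed to compute all three outcomes, and body weight is needed for calculated loss. Every woman who has the outcome therefore has the covariate.

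At stake is the width of the intervals for these three outcomes and the power to see modest effects on them. The gain would also carry into the planned analysis of secondary outcomes among women delivered during labour, where fewer women contribute. Timing matters because the trial is open-label: adjustment added after outcome data have been seen would be post hoc.

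**Working it through.** **Inputs.** From Sample size: 581 per arm, 1:1, two-sided 5%, rates of 2.1% and 5.8%. From the Literature review: a pooled haemoglobin effect of 0.61 g/dL and a pooled blood-loss effect of 160.27 (no unit given, read as mL). All SDs and correlations below are assumptions.

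**The plan's own figure.** The Fleiss formula with the plan's rounded z-values gives
(1.96 × √(2 × 0.0395 × 0.9605) + 1.28 × √(0.021 × 0.979 + 0.058 × 0.942))² / 0.037² = 579.8.
Unrounded z-values give 581, as stated. This figure is for the binary primary outcome. The plan gives no precision figure for the continuous outcomes.

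**Change scores.** Let ρ be the correlation between the pre- and post-operative values, and k the post/pre ratio of SDs. In units of the pre-operative variance:

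- change score: 1 + k² − 2ρk
- ANCOVA: k²(1 − ρ²)
- difference between them: (1 − ρk)², which is never negative.

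With k = 1 the variance ratio, ANCOVA to change score, is (1 + ρ)/2. The last column is 581 divided by that ratio.

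| ρ | Variance ratio | SE smaller by | Equivalent women per arm |
|---|---|---|---|
| 0.5 | 0.75 | 13.4% | 775 |
| 0.6 | 0.80 | 10.6% | 726 |
| 0.7 | 0.85 | 7.8% | 684 |
| 0.8 | 0.90 | 5.1% | 646 |
| 0.9 | 0.95 | 2.5% | 612 |

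With unequal SDs and the same range of ρ, the variance ratio is 0.571–0.640 at k = 0.8, 0.668–0.810 at 0.9, 0.818–1.000 at 1.1 and 0.871–0.997 at 1.2. The SE is therefore 0 to 24% smaller. The gain vanishes where ρk = 1, for example near k = 1.1 and ρ = 0.9.

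**Detectable haemoglobin difference, 80% power.** (1.96 + 0.84) × SD × √(2/581) is 0.16 to 0.25 g/dL for an SD of change of 1.0 to 1.5 g/dL. It becomes 0.14 to 0.21 at ρ = 0.5 (× 0.866) and 0.16 to 0.24 at ρ = 0.9 (× 0.975).

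**Calculated loss.** This is a ratio multiplied by weight, so it was simulated: pre-operative haematocrit mean 35 and SD 3–4, fall of 2–4 points, ρ 0.5–0.9, weight 75 kg (SD 13). With equal SDs, residual over total variance is 0.793–0.999 after adjusting for haematocrit and 0.785–0.956 with weight added. The SE is then 0–11% and 2–11% smaller. Over k = 0.8 to 1.2 the variance ratios are 0.629–1.000 and 0.616–0.986. A separate simulation with 581 per arm (mean 36, SD 3.5, fall 3.5) gave interval widths of 0.91, 0.96 and 1.00 times the unadjusted width at ρ = 0.5, 0.7 and 0.9. With weight added they were 0.89, 0.94 and 0.94.

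**Cost of the covariates.** With three covariates, (N − 3)/(N − p − 3) = 1159/1156 = 1.0026, a variance inflation of 0.26%.

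**Does it change a conclusion at the cited effects?** Unadjusted z for haemoglobin is 0.61/0.0587 = 10.4 at SD 1.0 and 0.61/0.0880 = 6.9 at SD 1.5. For loss it is 160.27/23.5 = 6.8 at SD 400 mL and 160.27/35.2 = 4.6 at SD 600 mL. It does not.

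**Primary outcome.** At the design rates, with an assumed labour share of 0.5–1.0, labour odds ratio of 1.5–5 and haematocrit odds ratio of 1–2 per SD, adjustment lowers the variance of the risk difference by 0 to 4.3%. That is negligible.

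**Women without a calculated loss because of transfusion.** Transfusion for PPH is one component of the primary outcome, so the primary event count is a ceiling. At design rates it is 581 × (0.021 + 0.058) = 45.9 women, or 4.0% of 1,162. At the pilot's per-protocol rates it is 581 × (0.226 + 0.314) = 314 women, or 27%. The documents do not split events by component.

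**The case against.** The planned comparisons are legitimate and unbiased, only secondary outcomes are concerned, and at the cited effects significance does not depend on adjustment. The size of the gain rests on correlations and SDs that the documents do not give, and it can be nil. In the second simulation, raising the post-operative SD from 3.5 to 4 cuts the gain at ρ = 0.7 to about 3% for change and 1% for calculated loss. All of this stands. It is why the point is put as a free improvement and why the gain is described as usual, not certain.

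Further objections are fair in part:

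- The detectable differences use 1.96 and ignore Benjamini–Hochberg, so in absolute terms they are optimistic. The relative gain is unaffected.
- The pooled 160 mL effect comes from trials that measured blood loss in different ways, as the Literature review itself warns. It is only a rough guide for haematocrit-based loss.
- The handling of transfused women is a question of missing outcomes, which ANCOVA does not repair. The plan openly says their loss cannot be determined and counts them in the primary outcome. It does not say how they enter the mean, so that gap needs its own sentence.
- Regression needs a rule for when the Wilcoxon test would apply instead. That is accepted and included in the fix.

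**Conclusion.** The point holds as a recommendation on efficiency. The three outcomes are to be analysed unadjusted, the pre-operative value is part of each, and in large samples ANCOVA on the same data cannot be less precise. Under the assumed correlations of 0.5 to 0.9, the standard error for the change scores falls by 13.4% to 2.5% with equal SDs, and by 0 to 24% with SD ratios of 0.8 to 1.2. For calculated loss with equal SDs it falls by 0 to 11%, or 2 to 11% with weight added. The benefit is narrower intervals and better power for effects smaller than those cited. The primary analysis and the 581 per group are not in question.

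**What to change.** Amend Statistical methods and data reporting before outcome data are seen:

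1. For haemoglobin change and haematocrit change, prespecify ANCOVA with treatment, the corresponding pre-operative value and hospital.
2. For mean calculated blood loss, prespecify linear regression with treatment, pre-operative haematocrit, hospital and, optionally, body weight.
3. State that these models give the main estimate for the three outcomes and that the Wilcoxon test is a sensitivity analysis, so that the choice is not made after looking at the data.
4. Add one Wilcoxon sensitivity analysis of calculated loss in which transfused women receive the worst rank. Otherwise women who are probably among the heaviest bleeders drop out of the mean, possibly unequally by arm. State also how a post-transfusion haemoglobin or haematocrit enters the change scores.
5. Add labour status only if it is recorded before randomisation and varies enough. The documents do not say when women are randomised, and consent may precede labour. With emergency caesarean as a proxy, the Feasibility figures give a share of 460/600 = 77% before COVID (reading the 210 at the second hospital as emergencies) and (154 + 149)/303 = 100% during it. At 100% the covariate carries no information.
6. Leave the primary analysis unadjusted. An adjusted estimate is at most optional and supportive.

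The cost is SAP wording and a few lines of Stata. No new data are needed, and no missing-covariate rule for the pre-operative value or weight. The sample size does not change.

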Simonazzi et. al. analysed 2345 caesarean deliveries. Compared with patients who did not receive TXA, the study group had significantly less blood loss, (-160.27; 95% CI, -224.63 to-95.92), a lower drop in haemoglobin (-0.61 g/dL; 95% CI, -1.04 to -0.18), and a lower incidence of PPH and severe PPH. They also had less need for additional uterotonics (4.2% vs 7.3%; RR, 0.54; 95% CI, 0.36–0.81). The percentage of patients requiring blood transfusion during or after caesarean delivery was significantly lower in the TXA group (1.9% vs 5.7%; RR,0.33; 95% CI, 0.19–0.58). The adverse outcomes showed no significant difference: 2 patients in the intervention group and 2 in the placebo group experienced thromboembolic events (Table 1). This study was unique in that it had broader inclusion criteria, including multiple gestation pregnancies, as well as both labouring and planned caesarean deliveries. However, clinical heterogeneity

may have conflicted the results due to differences in TXA dosing, timing of intervention, and methods for measuring blood loss among the included studies (18).

A widely referenced study by Wang et al is a large meta-analysis of 11 RCTs where TXA was administered before the start of scheduled caesarean deliveries. This study also showed that TXA intervention significantly reduced intraoperative blood loss during and after caesarean delivery without an increase in thromboembolic events; this reduction was similar for both 1 g dosing and weight-based TXA dosing regimens. Similar to the meta-analysis by Simonazzi et al, prophylactic TXA was associated with a lower incidence of PPH, a smaller drop in postpartum haemoglobin, and a reduced requirement for blood transfusion (6).

A third large meta-analysis of prophylactic TXA use at the time of caesarean delivery, published as a Cochrane Review, produced similar outcomes to other large meta-analyses. For scheduled elective caesarean deliveries, TXA use was effective in reducing the incidence of PPH and blood transfusion requirements. As in other studies, gastrointestinal adverse effects, such as nausea and vomiting, were the most common adverse outcomes. Of note, the authors concluded that the studies were too small and underpowered to detect the effect of TXA on risk of maternal death or thromboembolism (17).

Similar outcomes are described among small RCTs of TXA use before caesarean delivery (19–23).

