 - iii. sensation of rings or spots of light in visual field
 - iv. dizziness
- c. the occurrence of potential severe adverse effects of TXA during the hospital stay and up to discharge
 - i. deep vein thrombosis, if the diagnosis is confirmed by Doppler ultrasound
 - ii. pulmonary embolism, if the diagnosis is confirmed by radiological examination
 - iii. myocardial infarction
 - iv. seizure
 - v. renal failure requiring dialysis
- d. any other unexpected adverse events

Data Management

The researcher and assistants will allocate each patient codes. No identifiers will be used. Any data collected will be stored in an office accessible only to the researcher and research assistants, as well as on a password-protected laptop computer.

data cleaning and entry

Completed questionnaires will be checked for validity, accuracy and completeness by the principal investigator before data entry into the computer.

Statistical methods and data reporting

Data analysis and reporting will be guided by the Consolidated Standards of Reporting Trials (CONSORT) and will be done by the researchers with the assistance of the statistician. (34).

The women's demographic characteristics and standard risk factors for PPH will be compared between the two groups.

The main analysis of the primary and secondary outcomes will be performed in the modified intention-to-treat (ITT) population, defined as women who undergo randomization and have a caesarean delivery (except if they withdraw consent or are deemed ineligible after randomization).

We will also analyse two separate per-protocol populations: women from the modified ITT population receiving a uterotonic and TXA (as specified in the protocol) (per-protocol group 1); the other will include women from the modified ITT population receiving a uterotonic and then tranexamic acid or no TXA in the 10min after delivery (per-protocol group 2; for a situation more consistent with routine clinical practice). The baseline characteristics of the trial participants, the management of the third stage of labour, and protocol adherence will be compared by descriptive statistics.

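### The subgroup plan tests TXA inside two nested high-risk groups, with no estimate for the other women and no interaction, so it cannot show that the effect differs between women

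*Combined protocol and SAP*

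**What the plan says.** All of this is in the combined protocol and SAP, mostly under Statistical methods and data reporting.

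- Overall analysis: "The main analysis of the primary and secondary outcomes will be performed in the modified intention-to-treat (ITT) population". Effects are given as relative risks and absolute risk differences with 95% CIs for binary outcomes, and as mean differences for quantitative ones.
- Subgroups for the primary outcome: "Two specified subgroup analyses will examine the primary outcome in subgroups of women at high risk of PPH". The first is caesarean during labour. The second is a composite, defined as "having at least one risk factor with an odds ratio of 3 or greater in the literature", with the list "history of any of PPH, hypertensive disorder of pregnancy, multiple pregnancy, or caesarean during labour".
- Subgroups for the secondary outcomes: "prespecified subgroup analyses will examine the secondary outcomes in the subgroup of women who undergo a caesarean during labour".
- Multiplicity: Benjamini–Hochberg is named as the "procedure to adjust for multiple comparisons of secondary outcomes or subgroups".
- Population: the inclusion criteria admit "Elective or emergency caesarean delivery".

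No section plans a result for women not in labour or for women with none of the listed risk factors. None names an interaction term, a ratio of relative risks or a difference of risk differences.

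**The concern.** A test of TXA against control inside one group says whether there is evidence of an effect in that group. It does not say whether the effect differs from that in other women; that needs an estimate of the difference between groups. Benjamini–Hochberg limits false discoveries among the tests that are run, but it does not turn a within-group test into a between-group one.

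The last item in the composite list is the first subgroup, so every woman in the first is also in the second. A reader who sees both reach significance might count two confirmations where much of the data is the same.

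The women left without a planned estimate are also those closest to much of the cited evidence. The literature review says of one meta-analysis: "For scheduled elective caesarean deliveries, TXA use was effective in reducing the incidence of PPH and blood transfusion requirements". It describes a second as covering scheduled caesareans, while the third included labouring women. The title of the pilot's cited record refers to elective caesarean. A reader who wants to set the trial against that evidence would look first for the estimate outside labour.

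**Working it through.** **1. The structural point.** This needs no arithmetic. Set side by side, the definitions give two subgroups, both high-risk, the first contained in the second. Neither complement is analysed and no contrast between levels is named. The wording about what the subgroups include is slightly loose, but the number is fixed at two and both are defined.

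**2. The plan's own figure.** The sample size section gives 581 per group for 2.1% versus 5.8%, two-sided 5%, 90% power. With unrounded normal quantiles the stated formula returns 581 and power at 581 is 90.0%. (The printed z values of 1.96 and 1.28 give 579.8.) The sample size stands.

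**3. Inputs for an illustration.** From the plan: control risk 0.058, TXA risk 0.021, 581 per arm, so a relative risk of 0.021/0.058 = 0.362. Assumed: the share of women in labour, which the documents do not state. I use 50%, 77% and 90%. The 77% comes from the pre-COVID monthly figures under Feasibility: (250 + 210)/(60 + 250 + 80 + 210) = 460/600 = 76.7%. It is only a proxy, because emergency is not the same as labour and the 210 is not labelled as emergency. Also assumed: the same control risk and the same relative risk in both groups.

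**4. Formulas.**

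- Expected events outside labour = n_out × (0.058 + 0.021).
- Variance of the log ratio of relative risks = [(1 − 0.021)/0.021 + (1 − 0.058)/0.058] × (1/n_in + 1/n_out) = 62.86 × (1/n_in + 1/n_out), with n per arm.
- Expected 95% CI around a ratio of 1 = exp(±1.96 × SE).

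| Assumed labour share | n per arm, in / out | Events outside labour | SE | 95% CI for ratio of relative risks |
|---|---|---|---|---|
| 50% | 290 / 291 | 23.0 | 0.658 | 0.28 to 3.63 |
| 77% | 447 / 134 | 10.6 | 0.781 | 0.22 to 4.62 |
| 90% | 523 / 58 | 4.6 | 1.097 | 0.12 to 8.59 |

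**5. Why a within-group p-value is not a comparison.** With an identical effect in all women, approximate power inside labour is 63/81/87% and outside labour 63/34/17% at the three shares. The two groups share no women, so the chance that labour is significant and the remainder is not is about 0.63 × 0.37 = 23%, 0.81 × 0.66 = 53% and 0.87 × 0.83 = 72%. An apparent labour-only effect would then arise from group size alone.

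**6. How far nested results repeat each other.** With equal risk, the correlation between a test in a subgroup and a test in a larger group containing it is the square root of the ratio of their sizes. For labour against all women this is √0.50 = 0.71, √0.77 = 0.88 and √0.90 = 0.95. The composite lies between the two in size, so labour against composite is correlated at least this strongly.

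**7. What an interaction test could detect.** If TXA had no effect at all outside labour (control risk 5.8% in both groups), power is Φ(1.016/SE − 1.96), where 1.016 = −ln 0.362 and SE² = 62.86/n_in + 2 × 16.24/n_out. This gives about 43%, 38% and 23%.

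**The case against.** The research question and objectives ask for the overall effect only, and the plan sets out to examine high-risk women, which is a within-group question. The subgroups are prespecified and a multiplicity procedure is named. All of that stands, and it keeps the point minor.

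Two stronger readings are tempting and the documents do not support them. A reader might infer that TXA is analysed only in high-risk women. It is not: the main analysis covers the whole modified ITT population, and only the subgroup plan is restricted. A reader might also infer that results for the other women are lost. They are largely recoverable: counts can be obtained by subtraction, and so can means and standard deviations when group sizes are reported. Only outcomes summarised as medians cannot be recovered this way. The gap is that nobody is committed to showing the complement or the contrast.

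The best remaining objection is that the interaction would be too imprecise to be useful. The table concedes most of this. The group outside labour could even be smaller than assumed: the COVID-period figures used to project recruitment, 154 + 149 = 303 a month, count emergency caesareans only, although the plan expects elective work to recover. But a wide interval tells the reader that the data cannot separate the groups, which a lone subgroup p-value conceals. The objection does carry weight against interaction tests for rare secondary outcomes such as death or ICU transfer; these would be uninformative and are not asked for.

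**Conclusion.** The concern holds as an omission in the subgroup plan and is minor. As written, no planned output compares the effect of TXA between women in labour and others, or between women with and without the composite risk, and the two nested results cannot count as separate evidence. It would be wrong to infer that the plan claims a differential effect or contradicts itself; it does neither. The primary analysis and the 581 per group are unaffected.

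The structural conclusion rests on the text alone. The numbers rest on assumed labour shares, equal control risk and the planned rates. If risk is lower outside labour, or fewer women fall there, events would be fewer and the intervals wider than shown.

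**What to change.** For the primary outcome, state in the SAP that:

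- for each factor (labour versus no labour; composite risk versus none), the relative risk and risk difference with 95% CI will be reported in both levels;
- the ratio of relative risks with 95% CI will be reported, using a named sparse-data method such as an exact or penalised-likelihood model;
- any claim of a differential effect will rest on that interaction alone;
- the subgroup results are exploratory, and the two subgroups are nested and not independent evidence;
- a non-significant interaction will not be read as proof of a uniform effect.

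For the secondary outcomes, show descriptive results for women not in labour beside the labour results, without interaction tests for rare outcomes.

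This needs no new data and no change to the sample size, because the variables already define the subgroups. It costs a few sentences in the SAP and some extra table columns, and the interaction estimate will be imprecise.
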